5.1.2 Hypotheses and Statistical Methods for Secondary Objectives

5.1.2.1 Immunogenicity

5.1.2.1.1 Hypotheses

No hypotheses will be tested.

5.1.2.1.2 Statistical Methods

For descriptive purposes, the statistics presented in [Table 5.1](#) will be produced. Immunogenicity endpoints will be summarized by age group, in pooled age groups, and by vaccine group with 95% CIs. Assuming that \log_{10} transformation of the data follows a normal distribution, the \log_{10} (data) will be used for the statistical analysis, then antilog transformations will be applied to the results of calculations, in order to provide the results in terms of GMs. The following descriptive statistics will be displayed:

- GMTs for each strain at D0 and D28
- The geometric mean titer ratios (GMTRs): geometric mean of the post-vaccination/pre-vaccination ratio for each strain
- Seroconversion rates at D28 compared to the baseline titers at D0
- Proportion of subjects with titers $\geq 1:40$ (1/dilution [dil]) for each strain at D0 and D28
- Reverse cumulative Distribution of titers for each strain at D0 and D28 (eg, RCDCs of the titers)

In addition, immunogenicity data will be displayed using GMTs and seroconversion rates by subgroups of age (< 65 years, 65 to 74 years, 75 to 84 years, ≥ 75 years, and ≥ 85 years), sex, race, previous influenza vaccination status (received a seasonal influenza vaccine in the last past influenza season or not), at-risk condition, and baseline seropositivity status (seropositive and seronegative are defined as baseline antibody titer $\geq 1:10$ or $< 1:10$).

5.1.2.2 Safety

5.1.2.2.1 Hypotheses

No hypotheses will be tested.

5.1.2.2.2 Statistical Methods

Safety endpoints will be summarized by age group, in pooled age groups, and by vaccine group. Solicited reactions (solicited injection site and systemic reactions), unsolicited AEs, SAEs, and AESIs will be summarized. The main parameters will be described with 95% CIs (Clopper-Pearson method) (1)

5.1.3 Hypotheses and Statistical Methods for Observational Objectives

5.1.3.1 Immunogenicity by SN Method

5.1.3.1.1 Hypotheses

No hypotheses will be tested.

5.1.3.1.2 Statistical Methods

Neutralizing Ab titers will be measured for each influenza strain with the SN method.

The following endpoints will be described by age group, in pooled age groups, and by vaccine group with 95% CIs:

- Individual neutralization test (NT) Ab titer on D0 and D28
- Individual NT Ab titer ratio (fold rise in serum NT post-vaccination relative to D0) at D28
- Subjects with NT Ab titers ≥ 20 (1/dil), ≥ 40 (1/dil), ≥ 80 (1/dil) at D28
- Fold rise in NT Ab titer [post/pre] ≥ 2 and ≥ 4 at D28
- Detectable NT (NT Ab titer ≥ 10 [1/dil]) at D0 and D28

In addition, the descriptive summary of SN immunogenicity results will also be produced by:

- Serological SN status at baseline (< 10 and ≥ 10 1/dil)
- Previous influenza vaccination status

5.1.3.2 Immunogenicity by ELLA Method

5.1.3.2.1 Hypotheses

No hypotheses will be tested.

5.1.3.2.2 Statistical Methods

Anti-N1 and -N2 titers will be measured for the 2 influenza A strains using ELLA.

The following endpoints will be described by age group, in pooled age groups, and by vaccine group with 95% CIs:

- Individual ELLA Ab titer on D0 and D28
- Individual ELLA Ab titer ratio (fold-rise in serum ELLA post-vaccination relative to D0) at D28
- Subjects with ELLA Ab titers ≥ 20 (1/dil), ≥ 40 (1/dil), ≥ 80 (1/dil) at D28
- Fold-rise in ELLA Ab titer [post/pre] ≥ 2 and ≥ 4 at D28
- Detectable ELLA (ELLA Ab titer ≥ 10 [1/dil]) at D0 and D28

5.2 Analysis Sets

Three main analysis sets will be used: the PPAS, the FAS, and the Safety Analysis Set (SafAS).

5.2.1 Full Analysis Set

The FAS is defined as the subset of randomized subjects who received the study vaccine and had a post-vaccination blood sample. Subjects will be analyzed according to the vaccine group to which they were randomized.

For the assessment of the immune response by virus SN and ELLA method, the analysis will be performed on the subjects from the FAS randomized into the respective observational subsets (FAS-SN subset and FAS-NA subset). The FAS-NA subset is a subset of the FAS-SN subset.

5.2.2 Per-Protocol Analysis Set

The PPAS is a subset of the FAS. The subjects presenting with at least one of the following relevant protocol deviations will be excluded from the PPAS:

- Subject did not meet all protocol-specified inclusion criteria or met at least one of the protocol-specified exclusion criteria
- Subject did not receive vaccine
- Subject received a vaccine other than the one that he / she was randomized to receive
- Preparation and / or administration of vaccine was not done as per-protocol
- Subject did not provide the post-dose serology sample at V02 in the proper time window (ie, 28 to 35 days after vaccination) or a post-dose serology sample was not drawn at V02
- Subject received medications impacting or that may have an impact on the immune response (Category 2 or 3)

- Any other deviation identified during the study conduct and identified as relevant by the clinical team during data review, ie, indicated as excluding subjects from this analysis set in the manual deviations dataset.

5.2.3 Safety Analysis Set

The SafAS is defined as those subjects who have received the study vaccine and have any safety data available. All subjects will have their safety analyzed according to the vaccine they actually received.

Safety data recorded for a vaccine received out of the protocol design will be excluded from the analysis (and listed separately).

5.2.4 Other Analysis Sets

Enrolled Subjects

Enrolled subjects are subjects for whom a CRB has been created.

Randomized Subjects

A randomized subject is a subject for whom a vaccine group has been allocated.

5.2.5 Populations Used in Analyses

All subjects with data in the CRB will be taken into account in the description of the population (eg, the disposition, the demographic or baseline characteristics).

All immunogenicity analyses from the HAI method for primary and secondary objectives will be performed on both FAS and PPAS.

The safety analyses will be performed on the SafAS.

The observational objective analyses will be performed on subsets of the FAS (FAS-SN and FAS-NA subsets).

5.3 Handling of Missing Data and Outliers

5.3.1 Safety

Generally, no replacement of missing data will be done. Nevertheless, missing relationship will be considered as related at the time of the statistical analysis. No search for outliers will be performed. In all subject listings, partial and missing data will be clearly indicated as missing.

5.3.1.1 Immediate

For unsolicited non-serious systemic AEs, a missing response to the “Immediate” field is assumed to have occurred after the 30-minute surveillance period and will not be imputed.

For SAEs, missing or partially missing elapsed time from last vaccination recorded if within 24 hours will remain missing and not be imputed. Such SAEs will not be considered as immediate.

5.3.1.2 Causality

Missing causality (relationship) for unsolicited non-serious AEs and SAEs will be considered at the time of analysis as related to vaccination.

5.3.1.3 Measurements

Partially missing temperatures will be handled as described in [Section 4.4.1.1.1](#).

5.3.1.4 Intensity

For solicited reactions, missing intensities will be handled as described in [Section 4.4.1.1.1](#). For unsolicited non-serious AEs, missing intensities will remain missing and will not be imputed.

5.3.1.5 Start Date and Stop Date

Missing or partially missing start dates for unsolicited AEs will remain missing and not be imputed. If either the start or stop date is missing or partially missing, the time of onset will be considered to be missing. Nevertheless unsolicited AEs with missing time of onset will be included in analyses according to the visit collected.

Missing or partially missing stop dates for AEs (solicited reactions and unsolicited AEs) will remain missing and not be imputed.

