4.4.1.2.3 Time of Onset

Time of onset is derived from the start date of the unsolicited AE provided in the clinical database and the date of last vaccination:

- Start date of the unsolicited AE – date of vaccination.

The time of onset should be considered as missing only if one or both of the dates are missing or partially missing.

The unsolicited non-serious AEs will be analyzed “Within 28 days”, which corresponds to AEs with a time of onset between 0 and 28 days after vaccination or missing. An AE with missing time of onset will be considered to have occurred just after the vaccination indicated by the visit number, so will be included in these tables.

Note: Unsolicited AEs that occurred before vaccination (negative time of onset) or with a time of onset higher than defined above (> 28 days) will not be included in analysis, but will be listed separately.

Time of onset will be displayed as follows:

- D0-D3
- D4-D7
- D8-D14
- \geq D15
- Missing

SAEs will be analyzed throughout the study using the following periods:

- During post-Dose period (ie, within 28 days after the injection)
- During the 6-month follow-up period (ie, from 29 days after the injection until the last subject contact)
- During the study (ie, all SAEs that occurred during the study)

An SAE with missing time of onset will be considered to have occurred just after the vaccination indicated by the visit number, so will be included in these tables.

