4.4.1.2.4 Duration

Duration is derived from the start and stop dates of the unsolicited AE provided in the clinical database:

- Stop date of unsolicited AE - start date of unsolicited AE + 1.

The duration should be considered as missing only if one or both of the start and stop dates of the unsolicited AE is missing or partially missing.

Duration will be displayed by period as following:

- 1-3 days
- 4-7 days
- 8-14 days
- \geq 15 days
- Missing

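### SAP 5.3.1.5 makes time of onset missing when only the stop date is missing, contradicting SAP 4.4.1.2.3; an ongoing unsolicited AE with a known start would then be reported with onset 'Missing'

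*SAP*

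**What the plan says.** SAP 4.4.1.2.3 (Time of Onset) derives onset of an unsolicited AE by subtracting the vaccination date from the AE start date. Its missingness rule refers to those two dates: "The time of onset should be considered as missing only if one or both of the dates are missing or partially missing". The stop date plays no part.

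The same section sets the 28-day analysis of non-serious events. It takes "AEs with a time of onset between 0 and 28 days after vaccination or missing". Events that began before vaccination, or "with a time of onset higher than defined above (> 28 days) will not be included in analysis, but will be listed separately". For serious events it adds: "An SAE with missing time of onset will be considered to have occurred just after the vaccination indicated by the visit number".

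SAP 5.3.1.5 (Start Date and Stop Date), in the missing-data part of the SAP, gives a different rule: "If either the start or stop date is missing or partially missing, the time of onset will be considered to be missing". It continues: "Nevertheless unsolicited AEs with missing time of onset will be included in analyses according to the visit collected". On stop dates it says: "Missing or partially missing stop dates for AEs (solicited reactions and unsolicited AEs) will remain missing and not be imputed".

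The start/stop pair appears in one other missingness rule, that for duration in SAP 4.4.1.2.4: "The duration should be considered as missing only if one or both of the start and stop dates" are missing or partly missing.

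In the protocol, footnote a to section 9.2.1.3.3 treats an AE with no stop date as ongoing at the end of the study. Section 9.2.1.2 lists time to onset of unsolicited AEs among the secondary safety endpoints.

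**The concern.** Onset is fixed once the start date and the vaccination date are known. When an event ended, or whether it has ended, carries no information about when it began. A rule that discards a known onset because the end is unrecorded therefore gives a wrong result, and it conflicts with the word 'only' in 4.4.1.2.3.

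The trigger is not exotic: an AE still ongoing at last contact normally has no stop date, and the SAP does not impute one. Two programmers who each follow the SAP, one from 4.4.1.2.3 and one from 5.3.1.5, would put the same event in different rows of the onset table, and the text would not settle which is right. The loss is also selective, because it falls on events with no recorded end.

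There is a second effect. Because the 28-day table admits events with missing onset, the rule in 5.3.1.5 could bring in non-serious events whose known start lies outside the window.

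**Working it through.** No sample size, power or alpha figure bears on this point, so there is no plan figure to reproduce. The check applies the two rules to the same hypothetical events.

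**Inputs**

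- Vaccination date = D0.
- Rule A (SAP 4.4.1.2.3): onset = start − vaccination; missing only if the start or vaccination date is missing or partial.
- Rule B (SAP 5.3.1.5): onset is missing if the start or the stop date is missing or partial.
- Onset rows (SAP 4.4.1.2.3): D0-D3, D4-D7, D8-D14, D15 or later, Missing.
- 28-day table (SAP 4.4.1.2.3): onset from 0 to 28, or missing.
- Collection of unsolicited AEs runs to V02 (Protocol 5.1.1). V02 is D28 with a window of +7 days, so in-window visits fall from D28 to 28 + 7 = D35.

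**Results** (the first event has a stop date; the next three do not; the last has no start date)

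| Event | Rule A | Rule B |
|---|---|---|
| Start D5, stop D9 | 5 − 0 = 5, D4-D7 | 5 − 0 = 5, D4-D7 |
| Start D5, no stop date | 5 − 0 = 5, D4-D7 | Missing |
| Start D20, no stop date | 20 − 0 = 20, D15 or later | Missing |
| Non-serious, start D30, V02 on D33, no stop date | 30 − 0 = 30 > 28; listed separately; 28-day count 0 | Missing; 28-day count could be 1 |
| Start missing, stop D9 | Missing | Missing |

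The rules agree when both AE dates are complete and when the start date is missing. They differ when the start is known and the stop date is not.

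The D5 and D20 events stay in the 28-day table under either rule; only their onset row changes. The D30 event can change the count in that table, because rule B makes its onset missing and 4.4.1.2.3 admits missing onsets. The same route is open in principle to an event with a known start before vaccination.

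**Serious events.** Take an SAE starting on D120 with no stop date. Rule A gives 120 days, which is in the 6-month follow-up period. Rule B gives missing, and its placement then depends on wording. Read one way, 4.4.1.2.3 puts it just after vaccination, in the post-dose period. Section 5.3.1.5 places it by the visit at which it was collected, which may point elsewhere. This is an ambiguity to clear up, not a demonstrated error. The SAE total for the whole study is the same either way.

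**Consistency with the rest of the SAP.** Elsewhere a missing stop date affects length only: duration of unsolicited AEs (4.4.1.2.4) and overall number of days of solicited reactions (4.4.1.1.6). Section 5.3.1.5 stands alone in letting it affect onset.

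**The case against.** The best case against the point is that this is a drafting slip whose intended reading is easy to see. Section 4.4.1.2.3 is the dedicated derivation section, with the formula, the missingness rule and the display rows. The start/stop pair in 5.3.1.5 is the one that 4.4.1.2.4 uses for duration, so the sentence was probably meant to be about duration. A careful programmer would follow 4.4.1.2.3, and the misreported onset would then never appear. The out-of-window case is also narrow: it needs a start after D28 and no later than V02, and no stop date. The pre-vaccination case is rarer still, since pre-existing conditions are reported as AEs only if they worsen (Protocol 9.2.1.1). No safety hypothesis is tested.

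Much of this stands. The effects arise only if 5.3.1.5 is the section programmed; the slip is a plausible explanation, though an inference; and the reach is limited. It does not remove the defect. Section 5.3.1.5 is where the SAP handles missing dates, and Protocol 12.3.1 leaves those details to the SAP, so a programmer who follows it is following the plan. If the intended rule is obvious, correcting the sentence is uncontroversial.

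**Conclusion.** The concern holds. The two sections give incompatible rules for an unsolicited AE with a known start and no stop date, and nothing in the documents reconciles them. Followed as written, 5.3.1.5 reports a known onset as missing, and through the inclusion rule in 4.4.1.2.3 it could add out-of-window non-serious events to the 28-day table.

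The size cannot be computed, because the documents give no share of AEs without a stop date. It is likely small. Related AEs should be affected less: their stop dates are actively sought (Protocol 9.2.1.3.3, footnote a) and they are followed until they resolve, stabilise or become chronic (Protocol 5.1.4), although a stable or chronic event may still have no stop date.

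The effect is confined to descriptive safety tables on unsolicited AEs. Solicited-reaction onset comes from daily intensities (SAP 4.4.1.1.4) and is untouched, as are whole-study SAE totals and the primary immunogenicity analysis. It should be corrected because it concerns a named secondary safety endpoint and costs almost nothing to put right.

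**What to change.** In SAP 5.3.1.5, make time of onset missing only when the AE start date or the vaccination date is missing or partial, as in 4.4.1.2.3. State that a missing or partial stop date makes only duration missing, as in 4.4.1.2.4. Use the same placement wording in 4.4.1.2.3 and 5.3.1.5 for events whose onset is truly missing, and say which period receives a serious event of that kind. Then check that the derivation program follows the corrected rule, with test records that have a known start and no stop date, including one starting after D28.

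The cost is one or two SAP sentences and a program check. No data collection or clinical procedure changes.

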5.3.1.6 Action Taken

Missing actions taken will remain missing and not be imputed.

5.3.2 Immunogenicity

LLOQ and ULOQ management will be performed as described in [Section 4.4.1.3.5](#). No test or search for outliers will be performed.

No replacement will be done for missing values. Based on the previous QIV-HD and QIV-SD trials in this population, the amount of missing immunogenicity data is expected to be $\leq 5\%$ in this trial. Usually in vaccine trials, it seems generally reasonable to assume missing immunogenicity data are missing completely at random (MCAR) (2). Indeed, it is highly unexpected that the dropout (or any other reason for missing data) could be linked to the immune

response of the subject. Therefore, confirming the results of the PPAS for the primary analysis with the FAS would be satisfactory in terms of sensitivity analysis.

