### 12.2.1 Full Analysis Set

The FAS is defined as the subset of randomized subjects who received one dose of the study vaccine and had a post-vaccination blood sample.

For the assessment of the immune response by virus SN and ELLA method, the analysis will be performed on the subjects from the FAS randomized into the respective observational subsets (FAS-SN subset and FAS-NA subset). The FAS-NA subset is a subset of the FAS-SN subset.

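### SAP 5.3.2 offers PPAS/FAS agreement as the sensitivity analysis for missing titers, but neither set contains a vaccinated subject with no post-vaccination sample

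*SAP*

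**What the plan says.** - **Missing titers (SAP 5.3.2).** "No replacement will be done for missing values"; "the amount of missing immunogenicity data is expected to be" no more than 5%; MCAR is taken as reasonable because a link between dropout and immune response is thought very unlikely. From this the section concludes that "confirming the results of the PPAS for the primary analysis with the FAS would be satisfactory in terms of sensitivity analysis". Protocol 12.3.2 likewise rules out imputation.
- **FAS (SAP 5.2.1).** "The FAS is defined as the subset of randomized subjects who received the study vaccine and had a post-vaccination blood sample". Protocol 12.2.1 sets the same condition: subjects who "received one dose of the study vaccine and had a post-vaccination blood sample".
- **PPAS (SAP 5.2.2).** "The PPAS is a subset of the FAS". Its exclusions cover eligibility, wrong vaccine, preparation or administration errors, a sample outside days 28 to 35, Category 2 or 3 medication, and the case in which the sample is absent ("or a post-dose serology sample was not drawn at V02").
- **Other sensitivity analysis (SAP 5.1.1.1.2).** An ANCOVA with the D0 HAI titer as covariate, run on the same two sets. Its stated purpose is to account for baseline variability.

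**The concern.** The final sentence of the missing-data paragraph rests on a comparison that holds no information about absent samples. V02 is the only planned post-vaccination draw. A subject vaccinated but not bled afterwards contributes to neither estimate, so the PPAS and FAS results can agree exactly whatever that subject's titer would have been. Both are complete-case analyses and share any bias that absent samples cause.

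The stake is limited but real. Superiority in an age group needs all 4 strains (SAP 5.1.1.1.1), and the overall objective needs all 4 in both age groups (SAP 5.1.1.1.2). One strain close to the threshold can therefore decide an age group's conclusion, and the stated check could not show whether that strain depends on its missing samples.

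**Working it through.** **1. Who is in which set.**

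| Vaccinated subject | FAS | PPAS |
|---|---|---|
| Sample in days 28 to 35, no deviation | yes | yes |
| Sample outside the window, or another listed deviation | yes | no |
| No post-vaccination sample | no | no |

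The two sets differ only in the second row. The third row is the missing-data problem, and it is outside both. The PPAS exclusion for a sample not drawn removes nobody further when there is no post-vaccination sample at all, because that subject is already outside the FAS.

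**2. What the ANCOVA adds.** With one post-baseline measurement, a complete-case ANCOVA is valid if missingness depends only on arm and D0 titer. That is weaker than MCAR. It does not cover missingness related to the unobserved D28 response.

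**3. The plan's own power figures.** Inputs from SAP 5.5: 385 per arm and age group, 5% attrition (385 × 0.95 = 365.75, taken as 365), GMT ratio 1.5 (log10 = 0.1761), SD 0.6 or 0.5, one-sided alpha 0.025. Power = Φ(0.1761 / (SD × √(2/365)) − 1.96).
- SD 0.6: Φ(3.965 − 1.96) = 97.75% (stated 97.7%).
- SD 0.5: Φ(4.758 − 1.96) = 99.74% (stated 99.7%).
- Overall, with 8 tests treated as independent: (0.9775² × 0.9974²)² = 90.4% (stated 90%).

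The inputs are therefore read as the SAP intends.

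**4. Tipping point.** Assumptions, not document figures: a fraction m is missing in each arm; missing QIV-HD subjects average δ log10 below observed QIV-HD subjects; missing QIV-SD subjects resemble observed ones; the observed standard error is kept; the SD given for QIV-SD applies to both arms. The effect in all vaccinated subjects is then log10(R) − mδ, and superiority is lost when

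δ = [log10(R) − 1.96 × SD × √(2/n)] / m.

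At m = 5%, n = 366 (365.75 rounded), and 1.96 × SD × √(2/366) is 0.0869 for SD 0.6 and 0.0724 for SD 0.5.

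| Observed ratio R | SD | δ (log10) | Fold |
|---|---|---|---|
| 1.5 | 0.6 | (0.1761 − 0.0869)/0.05 = 1.78 | 61 |
| 1.30 | 0.6 | (0.1139 − 0.0869)/0.05 = 0.54 | 3.5 |
| 1.25 | 0.6 | (0.0969 − 0.0869)/0.05 = 0.20 | 1.6 |
| 1.5 | 0.5 | (0.1761 − 0.0724)/0.05 = 2.07 | 118 |
| 1.30 | 0.5 | (0.1139 − 0.0724)/0.05 = 0.83 | 6.8 |
| 1.25 | 0.5 | (0.0969 − 0.0724)/0.05 = 0.49 | 3.1 |

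Range over m at SD 0.6: with 2% missing (n = 377), 26-fold at 1.30 and 3.7-fold at 1.25; with 10% missing (n = 346), 7.4-fold at 1.5, 1.8-fold at 1.30 and 1.2-fold at 1.25. An equal deficit with equal missingness in both arms cancels and leaves the ratio unchanged.

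**5. Error rate under the same model.** Suppose the true ratio in all vaccinated subjects is 1 and the 5% missing QIV-HD subjects are 0.3 log10 (2-fold) lower. Observed cases then show 10^(0.05 × 0.3) = 1.035 in both sets. The one-sided error for a single strain becomes 5.2% (SD 0.6) to 6.0% (SD 0.5) instead of 2.5%. This is per strain; the requirement for 4 strains makes a false claim for an age group harder.

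**6. How often a strain is near the threshold.** At a true ratio of 1.5 and SD 0.6, the standard error is 0.0444. The chance of succeeding with an observed ratio of 1.30 or less is Φ((0.1139 − 0.1761)/0.0444) − Φ((0.0869 − 0.1761)/0.0444), about 5.8%. For at least one of the four SD-0.6 comparisons it is 1 − (1 − 0.058)⁴, about 21%. This treats them as independent, which is rough because two strains are measured in the same subjects.

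**The case against.** The strongest reply is that 5.3.2 never says the FAS tests MCAR. It argues that missingness is small and unrelated to response, cites a reference, and infers that nothing more is needed. That reading is possible. The sentence still names FAS confirmation as the sensitivity analysis, inside a paragraph about missing values, and on the definitions it cannot serve as one.

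Several further points stand:
- The FAS requires a post-vaccination sample, not one inside the window. It restores late samples and Category 2 or 3 medication users that the PPAS drops, so the comparison is informative about those.
- The documents give no mechanism for arm-specific, response-linked missingness. Subjects and assessors are blinded with masked syringes (protocol 5.1.2 and 6.4), and a failed V02 draw may be repeated within the window (protocol 5.1.4). Protocol 1.2 says vaccine effectiveness depends on age, underlying conditions and immune competence. These might also affect attendance, but the documents do not show that they do, or that the effect would differ by arm.
- The 1.6-fold figure needs a near-threshold ratio, the larger SD, the full 5% missing and a deficit in QIV-HD only.
- Imputation, even as a supplement, departs from protocol 12.3.2 and has to be justified.

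A reader might infer that the plan has no protection beyond MCAR and that the primary conclusion is therefore unreliable. The documents do not support that: the ANCOVA already relaxes MCAR, and a result near the design ratio tolerates very large departures. Nor would the proposed tipping-point analysis test MCAR. It shows how far the missing values must depart before the conclusion changes. A table by baseline characteristics can contradict MCAR, but nothing in the observed data can exclude dependence on the unobserved response.

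**Conclusion.** The concern holds in limited form. PPAS versus FAS is a check on protocol deviations, not on absent samples, and SAP 5.3.2 describes it wrongly. The ANCOVA narrows the gap without closing it. The conclusion about set membership follows from the definitions alone and does not depend on which set carries the primary conclusion.

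The size rests on the assumptions in step 4 of the working. The risk is small at 5% or less missing and ratios near 1.5. It is material for an SD-0.6 strain observed at about 1.25 to 1.30, for an SD-0.5 strain observed somewhat lower (1.4-fold at a ratio of 1.20), or if missingness exceeds 5% or is unbalanced between arms. A near-threshold strain would decide at least its own age group's conclusion, and the overall objective with it. This should be corrected, but it does not threaten the design.

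**What to change.** 1. Reword SAP 5.3.2 so that PPAS versus FAS is described as the protocol-deviation check, including sample timing.
2. Tabulate missing D28 titers by arm, age group and baseline characteristics (D0 titer, sex, prior-season vaccination).
3. Add one supplementary analysis in all randomised and vaccinated subjects. Multiply impute D28 log10 titer by arm and age group from D0 titer, sex and prior-season vaccination, then apply a delta shift to the imputed QIV-HD values, per strain and age group, and report the shift at which superiority is lost.
4. Keep the primary analysis without imputation. Record the addition in SAP 5.7 as a supplementary departure from protocol 12.3.2.
5. Settle this before the blind is broken for the first analysis, because a tipping-point rule chosen afterwards carries less weight.

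The cost is a few hours of programming and a short justification. All the variables are already planned for collection; the sample size of 1540, the alpha and the primary test do not change.
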